Management of Care - Aim 2: To collaborate with 10 AA churches to train 30 church-based AA young adults as health advisors to master information about COVID-19 and its impact on the daily life of underserved AAs, particularly, older adults with underlying multimorbidity or social isolation; and Aim 3: To jointly implement and evaluate a telehealth-based, multidisciplinary, culturally-sensitive intervention with 265 AA older parishioners: (i) To mitigate the negative impact of COVID-19 on the management of chronic health conditions, and (ii) to reduce healthcare avoidance behaviors and psychological distress. This part includes two phases. **Phase 1** will utilize a community partnered participatory approach that will be specifically tailored to the education of church-based advisors. **Phase 2** will implement "one group pretest–posttest" design to improve COVID-19 associated health outcomes of AA older parishioners in collaboration with trained health advisors. Due to the disproportionate burden of COVID-19 on the AA community, every older adult who participates in this study would be identified as being at high risk for COVID-19 diagnosis and poor health outcomes associated with the disease. We cannot deprive or prevent this intervention for anyone at risk for COVID-19. Moreover, conducting a non-equivalent or a quasi-experimental design would be unethical.

Preliminary Studies: Our team has conducted similar intervention studies among AA older adults focused on reducing non-adherence to medication regimens, polypharmacy, and inappropriate use of medication among underserved 740 AA older adults. [name] has conducted several community-based cross-sectional surveys and interventional studies among older AA adults and specifically 47 out of his 170 manuscripts directly examine the health status and health care utilization of underserved older AA adults.⁵²⁻⁹⁸ The co-investigators of this proposed project have worked together for the last four years and collectively published numerous manuscripts, which 63 of which focused on health disparities and 19 manuscripts focused on health

care utilization, physical and mental health, medication-related challenges, and management of pain and chronic conditions among older AA adults.^{52,54,57-59,61,63-71,73,74,81,99}

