
 Invites participants to identify their own challenges & find solutions for their concerns in preventing COVID-19 infection. Enhance self-efficacy of management of chronic health conditions. 	
 Self-identified support for self-management (such as religion or spirituality) Motivate to discuss the medication-related options, & their benefits & risks, with both physicians & pharmacists.
Behavior Skills/Facilitators	

 Provide skills for specific needs regarding telehealth & online access to services Objective & perceived abilities for minimizing risk of contracting COVID-19 while performing daily activities Train self-monitoring for COVID-19 symptoms Connect patients with community resources. 	
 Develop skills & habits to visit providers continually using telehealth. Promote adherence to a healthy life style. Objective & perceived abilities for acquiring, self-cueing, & conducting tasks for self-management of chronic conditions.
Adherence Behaviors	

 Getting prescription filled/refilled on time. On-time surveillance & monitoring (i.e., lab tests, routine & required screening procedures, etc.) Access to pharmacies & getting prescription filled/refilled on time Safe & effective use of primary care services 	
 Use of on-line services for making medical appointments, obtaining medication refills, etc. Adhere to special instructions for life-style modification, diet etc. Adhere to vaccination schedules for older adults Adhere to COVID-19 testing

participants to sign up for the study or provide the contact information of other potential AA older adults (parishioners' parents, siblings, etc.) who would be eligible and benefit from this intervention. **Exclusion**

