Intervention Strategies: We collaborate with AA church-based advisors trained in Phase 1 to deliver three-month longitudinal intervention to 265 older AA Parishioners. This intervention is composed of six 2-hour bi-weekly sessions that include lectures, discussions, followed by one-on-one “problem solving” consultations. Instead of an in-person approach, this intervention will be provided via telehealth. **Table 1** shows the curriculum of the proposed bi-weekly seminars/ intervention. This intervention uses a participatory, culturally sensitive, theoretical based (IMB), and multidisciplinary approach to reduce risk and enhance health for AA older adults. The longitudinal intervention includes: 1) Telehealth training; 2) COVID-19 risk reduction and testing; 3) health screening; 4) adherence to disease surveillance and monitoring (i.e., lab tests, routine and required screening procedures, etc.); 5) promoting adherence to medication refill and regimens; 6) promoting adherence to recommended life style behaviors; and 7) flu, pneumonia, & COVID (once available) vaccination.

Individualized Meeting: Trained health advisors will offer individualized monthly meetings to an assigned caseload of AA older participants, in addition to bi-weekly seminars, for individualized health assessments, coaching, and support meetings with the participants. The health advisors will assess the older participant's management of their chronic conditions by utilizing a standardized visit form during these meetings (for example, a diabetic patient must see and ere specialist every year – depending on type of chronic conditions, there is a standard recommendation for physician visits. They will also encourage and assist the participants in making appointments and/or facilitating communication with their primary care provider, getting their medication refilled, and getting tested for COVID-19. If the participant does not have a physician, we will provide a referral located in close proximity to the participant.

Informing Primary Care Providers: The primary care provider of participants will be notified in case of positive depression or high anxiety severity following screening; non-adherence to treatment or inability to access their treatment; and clinical presentation warranting emergent care. If the participant does not have a primary care provider, they will be referred to a one that is located in proximity of their location.

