Church-based Health Advisors and our Health Practitioner to Deliver Seminar and Workshop (Phase 2): The bi-weekly seminars will be peer-led and conducted by each church-based health educator within their church. In each seminar, one of our specialists will participates in delivering the main component of intervention. For example, the infectious disease expert will help individuals reduce the risk of acquiring COVID-19; the pharmacist will work with participants to enhance their medication adherence and remove barriers related to their refills; and the lifestyle coach will help improve participants' lifestyles; etc.

Hypotheses: As a result of this intervention, it is expected that: 1) A 30% improvement of chronic physical and mental disease management among AA older adults; 2) A 80% increase in knowledge, attitude, and behaviors of COVID risk among AA older adults; and 3) a 40% increase in COVID-19 testing and 4) a 70% increase in uptake of influenza and pneumococcal vaccinations among participants.

Survey Instruments: Per the instruction of this NOSI, we will adopt survey instruments recommended by the **phenX Toolkit and Public Health Emergency and Disaster Research Response**.¹¹⁴ The survey (developed by the Aging and Geriatric Research Institute on UF) includes Covid-19 related measures and Health status and health care utilization, quality of life, and other related variables. In addition, we will include several validated survey instruments that our research team has recently used among AA older adults to investigate health status, health care utilization, and adherence to drug regimes in South Los Angeles.

Sample Size and Data Analysis (Phase 2): We will use a pretest–posttest design, comparing our outcomes before and after the intervention, with a three-month interval. Since our outcomes are binary (COVID infection

status, use of services, medication non-adherence, etc.), we will use the McNemar test, the test of choice for analyzing binary matched-pairs data.¹¹⁵ For our power calculation, we assume that our primary outcome (poor adherence) will show a 36% relative change (considering a 22% baseline

TIMELINE: Activities & Timeline (Months)	1-3	4-6	7-9	10-12
Church leaders recruited	X			
CDC/States Guideline Implementation	X	X	X	X
Health Advisors recruited & trained	X	X		
AA older adults recruited		X	X	X
Baseline data collection (older AA)		X	X	X
IRBNet # 1663247-2 Approved by: CDU IRB				
Older AA Intervention implemented		X	X	

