Post intervention data collected & analyzed			X	X
Final reports & RO1 preparation				X

Approval Period: April 23, 2021 to

status). Assuming an alpha of 0.05, we calculate that a total sample of 240 study participants will be necessary to achieve 80% power.¹¹⁶ With 10% drop-out,^{117,118} we will need to enroll 265 individuals. We will conduct longitudinal follow-up assessments to document changes to compare with baseline measures. At the descriptive level, the distribution and frequency of all items will be examined. The main hypothesis of this study is significant improvement of binary and continuous outcomes from pre- to post- tests. In bivariate analysis, we will apply McNemar's test as well as paired t-test to examine improvement of the outcome over the course of the study. Conducting multivariate analysis, when outcome variables are dichotomous/binary, to explore the role of potential confounders and baseline health status, as determinants of response (change), we will apply logistic regression. However, for corresponding dependent variables that appear to be ordinal a logit link will be used in polytomous or ordinal logistic models. Additionally, for continuous outcomes, we will use GLM to determine statistical differences in the primary outcome measures, while controlling for potential confounders and covariates associated with the selected outcomes. It should also be noted that missing results over time will be accounted for in the analysis using an inverse probability weighting scheme based on a logistic regression model.

References:

4. Barrett RK. Dialogues in diversity: An invited series of papers, advance directives, DNRs, and end-of-life care for African Americans. *OMEGA-Journal of Death and Dying*. 2006;52(3):249-261.
6. Escher Jr AR. An Ounce of Prevention: Coronavirus (COVID-19) and Mass Gatherings. *Cureus*. 2020;12(3).

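### Influenza uptake (hypothesis 4) has no look-back window, due-for-vaccine denominator or calendar term, so the uncontrolled three-month McNemar comparison mixes season with programme effect in either direction

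*Combined protocol and SAP*

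**What the plan says.** The Hypotheses paragraph lists, as its fourth expectation, "a 70% increase in uptake of influenza and pneumococcal vaccinations among participants". It gives no baseline rate and does not say whether the increase is relative or absolute. The two vaccines are joined in one statement.

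Vaccination is also part of the programme. Intervention Strategies lists "flu, pneumonia, & COVID (once available) vaccination", and Table 1 has the item "Adhere to vaccination schedules for older adults". Neither gives a season, a recall period or a rule for who is due.

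On design, Sample Size and Data Analysis (Phase 2) states: "We will use a pretest–posttest design, comparing our outcomes before and after the intervention, with a three-month interval". Part Two describes a single group and rejects any comparison group on ethical grounds. For binary outcomes, "we will use the McNemar test, the test of choice for analyzing binary matched-pairs data", and again "we will apply McNemar's test as well as paired t-test to examine improvement of the outcome over the course of the study". The later regression step names potential confounders and baseline health status, but not calendar time.

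The timeline table puts baseline surveys in study months 4–12, the intervention in months 4–9 and post-intervention data in months 7–12. Study month 1 has no calendar date. The only calendar anchor is the ethics approval period starting April 23, 2021, which is not said to be month 1.

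**The concern.** McNemar's test compares the number of participants who change from no to yes with the number who change from yes to no. In a one-group design this says something about the programme only if, without it, changes in the two directions would balance. For influenza vaccine they would not. Whether someone can change, and in which direction, depends on where their three months fall in the calendar.

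With staggered entry, participants with very different opportunities to be vaccinated are pooled as if alike. A real effect could be diluted, a null programme could look highly effective, or an effective one could look harmful. Nothing in the stated analysis would show which had happened.

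**Working it through.** **No plan figure to reproduce.** The plan gives no power or sample size for hypothesis 4. Its 240 analysed (265 enrolled) is for poor adherence. I use N = 240 below only to set the scale. Season dates, coverage and timing are my assumptions, and so is the premise that the vaccine is repeated yearly and offered in only part of the year.

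**Usable baselines.** A pair needs a post-test three months after baseline, and the timeline ends at month 12. Baselines must therefore fall by the end of month 9 (9 + 3 = 12), so the usable window is months 4–9.

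**1. Off-season intervals.** Assume a September–January season and even monthly accrual, and count the entry month and the next two. Entries in February, March, April, May and June contain no season month. The share of the six entry months that is off-season, by calendar month of study month 1, is:

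| Month 1 | Entry months | Off-season |
|---|---|---|
| Jan | Apr–Sep | 3/6 = 50% |
| Feb | May–Oct | 2/6 = 33% |
| Mar | Jun–Nov | 1/6 = 17% |
| Apr | Jul–Dec | 0/6 = 0% |
| May | Aug–Jan | 0/6 = 0% |
| Jun | Sep–Feb | 1/6 = 17% |
| Jul | Oct–Mar | 2/6 = 33% |
| Aug | Nov–Apr | 3/6 = 50% |
| Sep | Dec–May | 4/6 = 67% |
| Oct | Jan–Jun | 5/6 = 83% |
| Nov | Feb–Jul | 5/6 = 83% |
| Dec | Mar–Aug | 4/6 = 67% |

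The range is 0% to 83%. Sensitivity:
- Mid-month entry: June entrants reach mid-September and January entrants stay in season, leaving February–May off-season, so the maximum is 4/6 = 67%.
- Entry spread continuously over months 4–9: 0–83% for a September–December season, 0–50% for September–February and 0–17% for September–April.

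Dilution: observed gain = true gain × (1 − off-season share). With half the intervals off-season, a true 20-point gain shows as 20 × 0.5 = 10 points.

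**2. Early-season intervals.** Suppose the programme does nothing and current-season coverage rises from an assumed 10% at baseline to 40% three months later. Improving pairs = 240 × (0.40 − 0.10) = 72, with none worsening. McNemar z = (72 − 0)/√(72 + 0) = 8.5. Within one season nobody can go from yes to no, so even 6 new vaccinations in 240 (2.5%) give an exact two-sided p = 2 × 0.5⁶ = 0.031.

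**3. Intervals crossing a season change.** This depends on the item wording.
- *This season*: worsening pairs with no programme effect = 240 × share crossing × prior coverage × share not yet re-vaccinated. With 25–50% crossing, 40–70% coverage and half re-vaccinated, this runs from 240 × 0.25 × 0.4 × 0.5 = 12 to 240 × 0.5 × 0.7 × 0.5 = 42 pairs. If these are the only discordant pairs, |z| is √12 = 3.5 to √42 = 6.5.
- *Past 12 months*: an every-year vaccinator turns from yes to no if last year's dose fell before the post-test date and this year's falls after it. Assume 25/40/20/15% vaccinate in September/October/November/December. For mid-July entry (mid-October post-test), 25% + half of 40% = 45% have vaccinated by then. If timing is independent from year to year, 0.45 × 0.55 = 25% reverse. If instead the year-to-year shift has a standard deviation of two weeks, the share is about density × SD × 0.399 = (0.40/30.4) × 14 × 0.399 = 7%.
- *Ever vaccinated*: no reversals, but a repeat vaccinator can never register, so seasonal uptake is not measured.

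**The case against.** The strongest reply is that much of this is contingent. The document does not give the survey items, and the instruments may well fix a look-back window. If month 1 were April or May 2021, close to the approval date, entries would fall between July and January and no interval would miss the assumed season. Influenza is half of one secondary hypothesis; the primary outcome is poor adherence. These points stand, and they limit the claim. They do not remove it: no item wording makes an off-season interval informative, and an autumn start that avoids off-season intervals is exactly the one that credits ordinary autumn vaccination to the programme.

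A reader might infer four stronger things that the documents do not support.
- *Off-season participants cannot be scored.* They are scored, as uninformative concordant pairs.
- *Regular vaccinators are scored as worsening.* That needs *this season* or *past 12 months* wording, which the plan does not choose. Under the latter, the size depends heavily on how stable people's timing is (25% against 7% above).
- *At least a fifth of intervals are off-season whatever the start.* Spreading entry over all nine baseline months gives 2/9 = 22% to 5/9 = 56%, but baselines after month 9 cannot form a three-month pair within the timeline. With months 4–9 the minimum is 0%.
- *Most discordant pairs are set by entry month.* The inputs needed to compute this are not in the documents.

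**Conclusion.** The point holds in a limited form. The influenza part of hypothesis 4 is left undefined on look-back, denominator and calendar time, and is assigned to an uncontrolled before-after test in all participants. Such a test cannot separate season from programme, and the bias can run either way. The off-season share is 0% to 83% under an assumed September–January season, even accrual and baselines in months 4–9; which value applies depends on a start date the plan does not give. The early-season and season-crossing figures illustrate direction and scale under assumed coverage and do not predict this trial. The finding does not touch the 240/265 sample size or the primary outcome. It should be corrected, but it does not threaten the trial's main analysis.

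**What to change.** 1. Separate influenza from pneumococcal, with its own definition, and drop the all-participant McNemar test for influenza.
2. At both surveys, record whether the current-season influenza vaccine has been received, and in which month.
3. Define the outcome as receipt between the pre- and post-survey, among participants not yet vaccinated for that season whose interval includes a period when vaccine is offered.
4. Report the proportion newly vaccinated with a confidence interval, by calendar month of entry, with the numbers set aside as already vaccinated or off-season.
5. Restate the influenza part of the 70% target on this proportion.
6. Present the result descriptively. Without a control group the proportion still includes people who would have been vaccinated anyway, so it should not be attributed to the programme.

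The cost is SAP wording and one or two survey items, with no extra participants or visits. The price is a smaller influenza denominator and a less flattering headline than a percentage increase in everyone. If the vaccination month is not collected, the ambiguity cannot be reliably repaired afterwards.

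### COVID infection status is tested pre-post for improvement without a definition: if it means ever infected it can only worsen, and if it means recently infected the programme's own testing drive distorts it

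*Combined protocol and SAP*

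**What the plan says.** Under Sample Size and Data Analysis (Phase 2) the design is stated as follows: "We will use a pretest–posttest design, comparing our outcomes before and after the intervention, with a three-month interval". The next sentence begins "Since our outcomes are binary (COVID infection" and continues "status, use of services, medication non-adherence, etc.), we will use the McNemar test". The same section then gives the direction of the test: "The main hypothesis of this study is significant improvement of binary and continuous outcomes from pre- to post- tests".

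The description of Part Two calls this a "one group pretest–posttest" design, and there is no comparison group.

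Testing is part of what is delivered. Intervention Strategies lists "2) COVID-19 risk reduction and testing" among the components, together with COVID vaccination once available. Under Individualized Meeting, advisors help participants with "getting their medication refilled, and getting tested for COVID-19". The Hypotheses paragraph expects "a 40% increase in COVID-19 testing" and does not say whether that is relative or absolute.

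The supplied text does not say whether infection status means ever, recent or current, and gives no recall window. The survey description refers only to COVID-related variables in Part A, which is used both before and after. No ascertainment independent of the programme and no adjustment for testing is described. The primary outcome in the power calculation is poor adherence, and none of the four numbered hypotheses concerns infection.

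**The concern.** McNemar's test compares participants who change from yes to no with those who change from no to yes. It suits a state that can change in both directions and is measured in the same way at both times. Adherence can meet the first condition. Infection status may fail either one: a lifetime item cannot reverse, and a recent-infection item depends on how much testing was done, which this programme sets out to change.

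The study's title is about reducing COVID-19 related risks, so a pre-post result on infection would attract attention. A protective programme could be reported as worsening infection status, or a waning epidemic wave could be reported as a benefit.

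**Working it through.** **Inputs.** From the plan: 240 pairs (its post-dropout sample size, derived for adherence), alpha 0.05 (taken as two-sided), a three-month interval and a 40% rise in testing. The plan has no figure for infection to reproduce. All infection risks and detection fractions below are assumptions, shown as ranges.

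**1. Ever infected.** The yes-to-no cell is zero apart from reporting error, so the probability of a significant improvement is 0 whatever the programme does. With k new infections and no reversals:

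- asymptotic: chi-square = (k − 0)²/k = k on 1 df; k = 4 gives p = 0.046 (k = 3 gives 0.083)
- mid-p: 2 × 0.5^k − 0.5^k = 0.5^k; k = 5 gives 0.031 (k = 4 gives 0.063)
- exact: 2 × 0.5^k; k = 6 gives 0.031 (k = 5 gives 0.063)

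The plan does not name a variant. The title of its McNemar reference (115) favours mid-p and asymptotic over exact conditional, so 4 or 5 is closer to the plan than 6.

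Only participants not infected before baseline can become new cases. The binomial chance of a significant worsening therefore depends on how many remain at risk: 240, or 216 or 192 if 10% or 20% were already infected.

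| Three-month risk | At risk | 4 or more (asymptotic) | 6 or more (exact) |
|---|---|---|---|
| 2% | 240 | 71% | 35% |
| 2% | 216 | 63% | 27% |
| 2% | 192 | 54% | 19% |
| 3% | 240 | 93% | 73% |
| 3% | 216 | 89% | 63% |
| 3% | 192 | 83% | 52% |
| 5% | 240 | 99.8% | 98% |

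So a programme that halves the risk from 4% to 2% would, with all 240 at risk, still show a significant worsening 71% of the time by the asymptotic test.

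**2. Infected in a recent window.** If detection is multiplied by m and the true reduction is r, the ratio of detected infections, after to before, is m(1 − r). It equals 1 at r = 1 − 1/m.

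- m = 1.4 (40% is relative and detection is proportional to testing): break-even r = 1 − 1/1.4 = 28.6%.
- m = 1.2 (detection rises half as much): break-even r = 1 − 1/1.2 = 16.7%.
- At m = 1.4, a true 20% reduction appears as 1.4 × 0.8 = 1.12, a 12% rise. A true 50% reduction appears as 1.4 × 0.5 = 0.70, a 30% fall.

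The rejection rates below use the asymptotic test, 240 pairs, m = 1.4, pre-intervention three-month incidence of 3% to 10%, baseline detection of 30% to 70%, and independence between the windows:

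- true 50% reduction: significant improvement in 4% to 17%
- true 10% to 20% reduction: significant worsening in about 3% to 11%
- no effect: significant worsening in 5% to 19%

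The error can also flatter the programme. With no effect and full detection at both times, a background fall in incidence from 10% to 5%, 10% to 2% or 5% to 1% gives a significant improvement in 56%, 98% or 76% of trials.

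**3. Currently infected.** Suppose prevalence is constant and every baseline case has recovered by post-test. New cases at post-test then balance the recoveries. At 2% prevalence there are on average 240 × 0.02 = 4.8 of each. By simulation at 1% to 5% prevalence, significant results occur in about 2% to 3% of trials in each direction, so recovery alone causes no bias. The difficulty is numbers: at prevalences of 0.2% to 2%, about 0.5 to 5 positives are expected at baseline, and power to detect a halving is 0.1% to 13%.

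**The case against.** Infection status appears once, in a parenthesis ending in etc. It is not the primary outcome or a numbered hypothesis, and no sentence commits the sponsor to claiming fewer infections. The survey comes from an external instrument that is not in the supplied text and may define the item. The lack of a control is a deliberate choice, defended in the description of Part Two, and epidemic timing affects other outcomes too. All of this stands, and it limits the weight of the point. It does not remove the point: the outcome is still listed for an improvement test. A definition in the survey would settle which reading applies, but none of the three readings gives a result that can be interpreted as a change in risk.

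Three stronger readings are tempting and are not supported:

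- A reader might infer that no wording of the item could ever show a fall. That is literally true only for ever infected; the other two can move both ways.
- A reader might infer that recovery from acute infection would masquerade as improvement. It does not, because new infections offset it.
- A reader might infer that a windowed item would often brand a protective programme as harmful. Under the assumptions above, a significant worsening is uncommon when the programme protects. The usual damage is an estimate that is masked or cannot be interpreted.

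**Conclusion.** The concern holds for this one non-primary outcome, and its size depends on a definition that the supplied text does not give. Under ever infected, the planned test has no chance of showing improvement, and 4 to 6 new infections, depending on the test variant, make it significant in the wrong direction. Under a recent window, a true reduction below about 29% is hidden or reversed. That figure assumes that the 40% is relative and that detection rises one-for-one with testing; a smaller rise in detection lowers it. A fall under this reading cannot be attributed to the programme, because there is no comparator and both the epidemic and vaccination were changing. Under currently infected, the test is not biased by recovery but is uninformative.

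A reader might infer that the trial's main result is compromised. The documents do not support that: the adherence outcome and its sample size do not depend on infection status. The point should be corrected before analysis, but it does not threaten the primary comparison.

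**What to change.** Take COVID infection status out of the outcomes tested by McNemar for improvement, and define the item and its recall window in the analysis paragraph. Among participants not previously infected at baseline, report new self-reported infections between baseline and post-test as a proportion with a 95% CI, beside the number tested in the same period. Label this descriptive and not evidence of a change in risk. Keep the pre-post tests for adherence and other outcomes that can move both ways.

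The cost is mainly wording. The post-test item must cover the period since baseline, or new infections must be derived from the paired answers. Because the same Part A is used at both times, a since-baseline item cannot be presumed, so the questionnaire should be checked before post-test collection. The trial gives up an inferential claim on infection that this design could not support.

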Strategies to Train AA Advisors: The workshop training will occur bi-weekly over a 3-month period to prepare them for delivering the intervention to AA older adults. Detailed information on the content areas are described in **Table 1**. The training curriculum will cover the following components: 1) minimize risk of COVID-19 infection and transmission; 2) utilizing remote learning platforms to train older adults on effective use of telehealth; 3) gain extensive knowledge regarding COVID-19 and its impact on individuals with underlying chronic conditions; 4) identify over-reacting (obsessive) and under-reacting behaviors to COVID-19, physical and social distancing, and other measures; 5) assessment of social needs and consequences of long-term social isolation; 6) delivery of extensive knowledge regarding the importance of adherence to medication refills and regimens, as well as adherence to lifestyle recommendations for older adults with chronic conditions; 7) providing functional support to older adults, particularly those who are socially isolated, to manage their activities of daily living; 8) assisting older adults in the use of online services for making medical appointments, obtaining medication refills, etc. and finally, 9) learn administering survey and collect data from older adults. In addition, we will discuss the functions and role expectations of health advisors, including care coordination, health coaching, education, and assessment, social support, and case management and resource linking.^{112,113}

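### The timeline recruits older adults through month 12 but marks the three-month intervention only in months 4–9, and the 265 has no margin for people enrolled too late to give a pre/post pair

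*Combined protocol and SAP*

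**What the plan says.** The Timeline table uses four three-month columns and ends at month 12. The rows that concern older adults are marked as follows.

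| Row | 1–3 | 4–6 | 7–9 | 10–12 |
|---|---|---|---|---|
| "AA older adults recruited" | | X | X | X |
| Row beginning "Baseline data collection (older AA" | | X | X | X |
| "Older AA Intervention implemented" | | X | X | |
| "Post intervention data collected & analyzed" | | | X | X |

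Under Intervention Strategies, the trained advisors are to "deliver three-month longitudinal intervention to 265 older AA Parishioners". Sample Size and Data Analysis (Phase 2) sets a pretest–posttest comparison with three months between the two measurements, a McNemar test for binary outcomes, 240 participants for 80% power, and 265 enrolled to allow for 10% drop-out. The same section plans inverse probability weighting for missing results. Neither a last-enrolment date nor expected accrual by quarter is given.

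**The concern.** The last recruitment quarter comes after the last intervention quarter. Someone who joins in months 10–12 has a baseline survey but no marked period in which to receive the programme, and the three-month post-test falls at or beyond the end of the table. The planned primary analysis uses only people with both surveys. If such people count toward the 265, the trial can report full enrolment and still fall short of the 240 pairs on which its power rests. Weighting can adjust for differences between those who do and do not give a post-test. It does not create pairs, and a person who never had access to the programme has no pre-to-post effect to recover.

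**Working it through.** **1. Which enrolment times fit the design.** Let t be the time of enrolment in elapsed months, so that month 10 begins at t = 9. Assume the programme starts at enrolment.

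- To finish a three-month programme within the marked intervention window (end of month 9): t + 3 ≤ 9, so t ≤ 6, the end of month 6.
- To give a three-month post-test within the table (end of month 12): t + 3 ≤ 12, so t ≤ 9, the end of month 9.

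This gives three groups:

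- Months 4–6: both conditions can be met.
- Well into months 7–9: the programme cannot finish in the marked window, but a post-test in months 10–12 is still possible.
- Months 10–12: no intervention is marked, and a post-test is possible only at the very end of the table, if at all.

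**2. The plan's 265.** 240 / 0.9 = 266.7 and 240 × 1.10 = 264, so 265 is reproduced to within rounding. In the other direction, 265 × 0.9 = 238.5 pairs. Drop-out alone uses the whole margin.

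**3. What late enrolment would cost (illustration).** From Sample Size and Data Analysis: baseline poor adherence 22%, relative change 36%, alpha 0.05, 240 participants, 80% power. My assumptions: the change is a reduction, the test is two-sided, only people enrolled in months 10–12 give no pair, and 10% of the rest drop out.

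- d = 0.22 × 0.36 = 0.0792, so the post-test rate is 0.1408.
- Power = Φ[(d√n − 1.96√p_D) / √(p_D − d²)], where p_D is the proportion of discordant pairs. The plan does not state p_D.
- Setting n = 240 and power = 80% gives p_D = 0.1937, a pre/post correlation of about 0.36.
- Pairs: n = 265 × (1 − L) × 0.9, where L is the share enrolled too late.

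| L | People late | Pairs | Power |
|---|---|---|---|
| 0 | 0 | 238.5 | 79.8% |
| 5% | 13 | 226.6 | 77.7% |
| 10% | 27 | 214.7 | 75.4% |
| 20% | 53 | 190.8 | 70.3% |

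Worked line for L = 10%: √214.65 = 14.65 and 0.0792 × 14.65 = 1.160. Then 1.96 × √0.1937 = 0.863 and √(0.1937 − 0.0063) = 0.433. So (1.160 − 0.863) / 0.433 = 0.69, and Φ(0.69) is about 75%.

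**4. Sensitivity.** At L = 10%, power is 57% if the correlation is 0 and 91% if it is 0.6. With nobody late the corresponding values are 61% and 94%. A one-sided test, with p_D recalibrated in the same way (0.246), gives 76% at L = 10%.

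**The case against.** **Accrual may be early.** Quarterly marks show when an activity may occur, not how many people it covers. If nearly everyone enrols by month 6, almost nothing is lost. This stands, and it is why no loss can be asserted. It does not remove the conflict, because the plan permits a full quarter of recruitment after the last intervention quarter and sets no cut-off.

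**Months 10–12 may be for Part B.** The diet, food-access and physical-activity survey is given at baseline only and needs no post-test. The documents do not say that the late marks are for this. Recruitment as well as baseline is marked there, and Part B is described as part of the pre-intervention survey.

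**The table may be unreliable.** An approval stamp and a page break interrupt it, and the point depends on single marks. The sponsor should confirm them. The other rows read sensibly, however (church leaders in months 1–3, final reports in months 10–12), and nothing suggests a misplaced mark.

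**The programme may be shorter than three months.** Six bi-weekly sessions span ten weeks from first to last, about 2.3 months. That moves the latest start for finishing by month 9 from t = 6 to about t = 6.7. It gives some slack in month 7 and none for months 10–12.

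**Advisor training.** A reader might infer a second conflict, since "Health Advisors recruited & trained" is marked through month 6, the course takes three months, and "The bi-weekly seminars will be peer-led and conducted by each church-based health educator within their church". The documents do not support this. Training is marked from month 1, so churches whose advisors train in months 1–3 can start in months 4–6, as the intervention row shows.

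**Conclusion.** The timeline contradicts the three-month pre/post design, and no other section resolves it. This rests on the row marks and the stated three-month durations, not on any power assumption.

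The size is unknown. With nobody late the plan keeps 238.5 pairs, in effect the intended 240. With 10% late it would have about 215 pairs and 75% power. That figure depends on an assumed late share and on a discordance solved backwards from the plan's own 240. Uncertainty about the correlation moves power far more than 10% late enrolment does, a loss of about 4 percentage points at the calibrated discordance.

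Two stronger readings are not supported:

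- A reader might infer that the 265 is miscalculated. It is not: it follows from 240 and 10% drop-out. The fault is that the schedule lets people count toward it who may be unable to give a pair.
- A reader might infer that a third of the sample is lost, because one of three recruitment quarters falls after the intervention. That would leave 265 × 2/3 × 0.9 = 159 pairs and 62% power, but it needs even accrual over months 4–12, which the documents nowhere state.

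**What to change.** Reconcile the recruitment, baseline, intervention and post-test rows with each other and with the three-month interval, in one of two ways:

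- State a last-enrolment date that leaves room for the three-month intervention and its post-test, with the 265 to be reached by then; or
- Extend the intervention and post-test rows to cover the people recruited last.

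In either case, count only people enrolled in time toward the 265 and the 240. Otherwise restate the expected pairs and power. If the months 10–12 marks are for Part B data only, say so and keep those people outside the 265.

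The cost is a tighter enrolment window or about three more months of follow-up, with no new measurements. Starting in month 4, closing enrolment at the end of month 9 needs 265 / 6 = 44 people per month and the intervention row extended into months 10–12. Closing at the end of month 6, with that row unchanged, needs 265 / 3 = 88 per month. The faster rate has a practical drawback: the trained advisors are to help recruit, and some may still be in training during months 4–6.
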